5.4.3 Reporting Requirements for Pregnancies

5.4.3.1 Pregnancies in Female Patients

Female patients of childbearing potential will be instructed to immediately inform the investigator if they become pregnant during the study or within 120 days of study drug administration. A paper *Clinical Trial Pregnancy Reporting Form* should be completed and submitted to the Sponsor or its designee immediately (i.e., no more than 24 hours after learning of the pregnancy), either by faxing or by scanning and emailing the form using the fax number or email address provided in [Section 5.4.2.1](#). Pregnancy should not be recorded on the Adverse Event eCRF. The investigator should counsel the

patient, discussing the risks of the pregnancy and the possible effects on the fetus. Monitoring of the patient should continue until conclusion of the pregnancy. Any serious adverse events associated with the pregnancy (e.g., an event in the fetus, an event in the mother during or after the pregnancy, or a congenital anomaly/birth defect in the child) should be reported on the Adverse Event eCRF. *In addition, the Investigator will submit a paper Clinical Trial Pregnancy Reporting Form when updated information on the course and outcome of the pregnancy becomes available.*

5.4.3.2 Pregnancies in Female Partners of Male Patients

Male patients will be instructed through the Informed Consent Form to immediately inform the investigator if their partner becomes pregnant *during the study or within 30 days of study drug administration. A paper Clinical Trial Pregnancy Reporting Form should be completed and submitted to the Sponsor or its designee immediately (i.e., no more than 24 hours after learning of the pregnancy), either by faxing or by scanning and emailing the form using the fax number or email address provided in Section 5.4.2.1.* Attempts should be made to collect and report details of the course and outcome of any pregnancy in the partner of a male patient exposed to study drug. The pregnant partner will need to sign an Authorization for Use and Disclosure of Pregnancy Health Information to allow for follow-up on her pregnancy. *After the authorization has been signed, the investigator will submit a paper Clinical Trial Pregnancy Reporting Form when updated information on the course and outcome of the pregnancy becomes available.* An investigator who is contacted by the male patient or his pregnant partner may provide information on the risks of the pregnancy and the possible effects on the fetus, to support an informed decision in cooperation with the treating physician and/or obstetrician.

5.4.3.3 Congenital Anomalies/Birth Defects and Abortions

Any congenital anomaly/birth defect in a child born to a female patient or female partner of a male patient exposed to study drug should be classified as a serious adverse event, recorded on the Adverse Event eCRF, and reported to the Sponsor immediately (i.e., no more than 24 hours after learning of the event; see [Section 5.4.2](#)). Any abortion should be reported in the same fashion (as the Sponsor considers abortions to be medically significant).

5.5 FOLLOW-UP OF PATIENTS AFTER ADVERSE EVENTS

5.5.1 Investigator Follow-Up

The investigator should follow each adverse event until the event has resolved to baseline grade or better, the event is assessed as stable by the investigator, the patient is lost to follow-up, or the patient withdraws consent. Every effort should be made to follow all serious adverse events considered to be related to study drug or trial-related procedures until a final outcome can be reported.

During the study period, resolution of adverse events (with dates) should be documented on the Adverse Event eCRF and in the patient's medical record to facilitate source data verification.

All pregnancies reported during the study should be followed until pregnancy outcome.

5.5.2 Sponsor Follow-Up

For serious adverse events, non-serious adverse events of special interest, and pregnancies, the Sponsor or a designee may follow up by telephone, fax, electronic mail, and/or a monitoring visit to obtain additional case details and outcome information (e.g., from hospital discharge summaries, consultant reports, autopsy reports) in order to perform an independent medical assessment of the reported case.

5.6 POST-STUDY ADVERSE EVENTS

The Sponsor should be notified if the investigator becomes aware of any serious adverse event that occurs after the end of the adverse event reporting period (defined as 60 days after the dose of study drug), if the event is believed to be related to prior study drug treatment. *These events should be reported through the use of the Adverse Event eCRF and submit the report via the EDC system. However, if the EDC system is not available, the investigator should report these events directly to the Sponsor or its designee, either by faxing or by scanning and emailing a paper Clinical Trial Serious Adverse Event / Adverse Event of Special Interest Reporting Form using the fax number or email address provided to investigators (refer to site binder).*

5.7 EXPEDITED REPORTING TO HEALTH AUTHORITIES, INVESTIGATORS, INSTITUTIONAL REVIEW BOARDS, AND ETHICS COMMITTEES

The Sponsor will promptly evaluate all serious adverse events including suspected unexpected serious adverse reactions (SUSARs) and non-serious adverse events of special interest against cumulative product experience to identify and expeditiously communicate possible new safety findings to investigators, IRBs, IECs, and applicable health authorities based on applicable legislation.

To determine reporting requirements for single adverse event cases, the Sponsor will assess the expectedness of these events using the following reference documents:

- MHAA4549A Investigator's Brochure
- Local prescribing information for oseltamivir

The Sponsor will compare the severity of each event and the cumulative event frequency reported for the study with the severity and frequency reported in the applicable reference document.

Reporting requirements will also be based on the investigator's assessment of causality and seriousness, with allowance for upgrading by the Sponsor as needed.

Certain adverse events are anticipated to occur in the study population at some frequency independent of study drug exposure and will be excluded from expedited reporting. These anticipated events include, but are not limited to, the following:

- Asymptomatic elevations of ALT, AST, and or amylase without corresponding elevations of bilirubin have been shown to be increased during influenza A infection ([Polakos et al. 2006](#); [Yingying 2011](#))
- Influenza associated disease and or complications of influenza

An IMC and SOC will monitor the incidence of the above-listed anticipated events during the study. An aggregate report of any clinically relevant imbalances that do not favor the test product will be submitted to health authorities.

6. STATISTICAL CONSIDERATIONS AND ANALYSIS PLAN

All efficacy analyses will be conducted according to the intent-to-treat principle and will include all patients who meet the following condition with patients allocated to the treatment arm to which they were randomized:

- Randomized patients who have confirmed influenza A infection as confirmed by a central PCR test from Day 1 samples

Safety analyses will include all patients who were included in the randomization and who received at least one dose of study medication, with patients allocated to the treatment arm associated with the regimen actually received.

No formal hypothesis testing will be done in this study. As a result, no adjustment for a type 1 error will be made to account for the multiplicity of analyses.

Results will be presented both for the MHAA4549A 3600 mg and 8400 mg treatment groups separately and combined for the purpose of comparison to standard of care.

Final efficacy and safety analyses of the total study population will be conducted at the end of the study after all patients have completed all study assessments and the database has been cleaned and closed. Further details of the analyses, including analysis of the exploratory endpoints, will be contained in the statistical analysis plan (SAP) which will be prepared and finalized before the first optional interim analysis (see [Section 6.10](#)) or the final efficacy and safety analysis, if no interim analysis takes place.

6.1 DETERMINATION OF SAMPLE SIZE

The purpose of this study is estimation of the effect size and hypothesis generation regarding the effect of MHAA4549A on the time to normalization of respiratory function relative to the standard of care rather than hypothesis testing. Point and interval estimates will be obtained. Approximately 330 patients will be enrolled. It is assumed that the median time to normalization of respiratory function in the control arm is 5 days. This sample size (approximately 110 patients per arm) provides 71% power to detect a

treatment difference of 1 day for the primary endpoint in both MHAA4549A arms assuming a 2-sided alpha of 0.2 and no difference in efficacy between the two active arms. If the 3600-mg dose shows a treatment difference of 1 day and the 8400-mg dose shows a treatment difference of 1.5 days or more then this sample size provides > 86% power assuming a 2-sided alpha of 0.2.

Operating characteristics (power) under other possible assumptions for 2-sided alpha of 0.2 and true differences of 0.5 to 2 days are provided in [Table 7](#).

Table 7 Operating Characteristics for Proposed Study Design for Several Possible True Underlying Median Values

	True Underlying Median for MHAA4549A							
	3600	8400	3600	8400	3600	8400	3600	8400
	mg	mg	mg	mg	mg	mg	mg	mg
	4 days	4 days	4 days	3.5 days	4 days	3 days	4.5 days	4 days
Hazard Ratio	0.8	0.8	0.8	0.7	0.8	0.6	0.9	0.8
Power of log-rank test ^a	71.4%		86.6%		98.8%		56.2%	

Note: Operating characteristics are based on the following assumptions: 330 evaluable patients, event times are exponentially distributed, median time to normalization of respiratory function in the control arm is 5 days, and patients are followed for 60 days.

^a Two-sided $\alpha = 0.20$.

It should be noted that the study is underpowered for detection of minimally clinically meaningful differences at a 2-sided alpha of 0.05 such as a true hazard ratio of 0.80 in both MHAA4549A arms.

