3.2.2 Rationale for Patient Population and Primary Endpoint

Severe influenza, for the purpose of this study, is defined as requiring one of the following treatments: any supplemental O₂ to maintain an SpO₂ > 92% or PPV. PPV is

defined as any mechanical positive pressure device to maintain oxygenation; this can include positive pressure mask and intubation.

This patient population was chosen based on the rationale that respiratory failure is a hallmark of influenza and a major driver of morbidity and mortality, as well as hospitalization. The recovery from ventilator support has been shown to be directly proportional to time spent in the ICU (Blackwood et al. 2011; Premier Inc, Charlotte, NC). Based upon an analysis of morbidity and mortality, the patient population that requires supplemental O₂ or ventilation on their first day of admission was determined to have a high unmet medical need as they have an estimated mortality of 9%-32%, and 27% require admission to the ICU, according to analysis of a database of over 70,000 hospitalized patients in the U.S. from 2005-2012 (Premier Inc, Charlotte, NC).

The proposed primary efficacy outcome measure in this study is “Time to normalization of respiratory function,” defined as oxygen saturation \geq 95% without oxygen supplementation. Support for use of a respiratory endpoint in this population comes from recently published data demonstrating that a composite endpoint that captured respiratory rate, fever, heart rate, and blood pressure resolution was primarily driven by the respiratory component of the endpoint (Marty et al. 2014). Given that influenza infections generally do not cause systemic infections and influenza disease is restricted to the respiratory tract, the Sponsor believes that the primary endpoint represents a clinically meaningful outcome in this patient population (as shown by analysis of PREMIER database) and measures an important physiologically relevant pharmacodynamic response parameter of MHAA4549A. This endpoint is a measure of patient function, measures a symptom that represents a serious consequence of influenza, and is consistent with clinically relevant endpoints discussed in the US Food and Drug Administration (FDA) Guidance, “Influenza: Developing Drugs for Treatment and/or Prophylaxis” (FDA 2011).

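### Section 6.1 and Table 7 give power for 330 evaluable patients although 330 is the enrolment target, and the 71% fits only the pooled comparison; each dose versus placebo has about 64%

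*Combined protocol and SAP*

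**What the plan says.** Section 6.1 (Version 7) sets the enrolment target: "Approximately 330 patients will be enrolled". With about 110 patients in each arm it claims 71% power. The effect to be found is described as "treatment difference of 1 day for the primary endpoint in both MHAA4549A arms", and the claim is conditional on two further settings, stated as "assuming a 2-sided alpha of 0.2 and no difference in efficacy between the two active arms". The control assumption is: "It is assumed that the median time to normalization of respiratory function in the control arm is 5 days". Table 7 gives log-rank power of 71.4%, 86.6%, 98.8% and 56.2% for four pairs of active-arm medians, with hazard ratios from 0.6 to 0.9. Its note reads: "Operating characteristics are based on the following assumptions: 330 evaluable patients, event times are exponentially distributed", with 60 days of follow-up.

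Section 6 restricts the efficacy analyses to: "Randomized patients who have confirmed influenza A infection as confirmed by a central PCR test from Day 1 samples". It also says that results will be shown for each dose and for the two doses combined, and that no formal hypothesis tests will be done. Section 4.1.1 admits patients on a Sponsor-approved antigen or PCR test. Section 4.9.1 does not replace withdrawals, and Section 6.4 censors patients lost to follow-up. Section 3.2.2 says of the target population that "they have an estimated mortality of 9%-32%, and 27% require admission to the ICU".

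**The concern.** Two things do not fit together. First, the number that drives the power calculation is the number evaluable, and it is set equal to the number enrolled. The current text makes no allowance for patients whose infection the central PCR does not confirm, for withdrawals, or for patients who never reach the event.

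Second, a three-arm trial has several possible log-rank comparisons: pooled active versus placebo, each dose versus placebo, or a three-group test. Neither Section 6.1 nor Table 7 says which one the power refers to. A reader who applies 71% to a single dose would think that dose better supported than it is.

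**Working it through.** **Inputs.** From Section 6.1: control median 5 days, exponential times, two-sided alpha 0.20 (z = 1.2816), 330 evaluable patients, 60 days of follow-up. Allocation is 1:1:1 (Section 4.2). Under exponential times the hazard ratio active/placebo is the inverse ratio of medians, so 4 versus 5 days gives 5/4 = 1.25 and ln 1.25 = 0.2231.

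**Events implied.** In the control arm the chance of no event by day 60 is 0.5^(60/5) = 0.0002. The table therefore assumes about 330 events.

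**Reproducing 71.4% (column 1, 4 days in both active arms).**
- Pooled active versus placebo (2:1), Freedman: sqrt(330 × 2) × 0.25/(1 + 2 × 1.25) = 1.835; 1.835 − 1.282 = 0.553; power 71.0%.
- The same comparison, Schoenfeld: sqrt(330 × 2/9) × 0.2231 = 1.911; power 73.5%. Simulated log-rank tests give about 72-74%.
- Three-group test, 2 df: noncentrality 330 × (2/9) × 0.2231² = 3.65, critical value 3.22; power 65.7% (simulated about 65-66%).
- One dose versus placebo (220 events): sqrt(220/4) × 0.2231 = 1.655; power 64.6% (Freedman 64.3%, simulated about 64-65%).

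Of these, only the pooled comparison comes near 71.4%.

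**The other columns, at 330 events.**

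| Medians, 3600 / 8400 mg | Stated | Three-group, 2 df | Pooled (Schoenfeld) | Pooled (simulated) |
|---|---|---|---|---|
| 4 / 4 | 71.4 | 65.7 | 73.5 | 72.6 |
| 4 / 3.5 | 86.6 | 86.8 | 88.5 | 87.0 |
| 4 / 3 | 98.8 | 98.6 | 96.9 | 95.7 |
| 4.5 / 4 | 56.2 | 56.8 | 55.0 | 53.5 |

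The three-group test matches columns 2 to 4 to within 0.6 points but misses column 1 by almost 6. The pooled test is near columns 1 and 2 but falls short in column 3, and by simulation also in column 4. Changing the event count does not help: a three-group test needs about 390 events to give 71% in column 1, and then gives about 91% and 62% in columns 2 and 4.

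**From enrolled to events (1-day benefit in both arms, alpha 0.20).** The documents do not give the non-evaluable share, so the values are assumptions shown as a range. Patients who never normalize are counted as having no event.

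| Not evaluable | No event | Events | Pooled, Freedman to Schoenfeld | Each dose, Schoenfeld |
|---|---|---|---|---|
| 0% | 0% | 330 | 71.0-73.5% | 64.6% |
| 5% | 0% | 314 | 69.4-71.9% | 63.0% |
| 10% | 0% | 297 | 67.7-70.2% | 61.3% |
| 20% | 0% | 264 | 64.0-66.6% | 57.9% |
| 0% | 9% | 300 | 68.0-70.6% | 61.7% |
| 10% | 9% | 270 | 64.8-67.3% | 58.6% |
| 10% | 32% | 202 | 56.1-58.4% | 50.5% |

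For example, 330 × 0.90 × 0.91 = 270 events.

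**Hazard ratios.** The listed 0.8, 0.7, 0.6 and 0.9 are ratios of medians, which under exponential times are placebo/active hazard ratios. As active/placebo they are 5/4 = 1.25, 5/3.5 = 1.43, 5/3 = 1.67 and 5/4.5 = 1.11.

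**The case against.** The strongest reply is that 71% is about right for a comparison the plan intends to present. Section 6 promises the doses combined, and Section 6.1 conditions the figure on equal efficacy of the two doses, which fits pooling. Nor does the pooled figure need every one of the 330 events: by Schoenfeld it is still 70-71% at 297 to 305 events. That stands, so the stated figure should not be called wrong as pooled power.

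A reader might infer that the protocol claims 71% power for both doses to succeed together, where the calculation gives about 49%. The documents do not support that reading. The reference to both arms can describe the assumed alternative, a 1-day effect present in each arm, and Section 6.1 uses it that way again for a hazard ratio of 0.80. What remains is that the comparison is not named.

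A reader might also take the 32% row as the expected result. It is a worst case. It stacks an assumed 10% loss on the top of a range from a US hospital database, while Section 4.1.2 excludes patients likely to die within 48 hours and Section 3.1.1 caps positive pressure ventilation at about 45%. It also counts every death as a lost event, although some may follow normalization.

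Finally, a reader might infer that the sponsor faces a lower chance of success, or that the listed 0.8 makes the planned Cox analysis wrong. The study is for estimation and defines no success criterion. The hazard-ratio point is one of labelling, since the medians beside it make the intended direction clear. Section 6.1 also already concedes low power at alpha 0.05.

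**Conclusion.** The point holds in this form. Section 6.1 treats the enrolment target as the evaluable number and assumes virtually all of those patients reach the event. Table 7 appears to mix tests without naming them: column 1 fits pooled active versus placebo, and columns 2 to 4 fit a three-group test that would give about 65% in column 1.

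For a 1-day benefit at two-sided alpha 0.20, each dose versus placebo has about 64% power even with all 330 events. Under an assumed 10% non-evaluable rate, pooled power is about 68-70% and each dose about 61%. With a further 9% never normalizing, the figures are about 65-67% and 59%. These results rest on exponential times, proportional hazards and equal allocation; the losses are assumptions, not forecasts.

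The effect on the pooled figure is modest. With no formal testing planned, it bears on how precision and per-dose support are described, not on a confirmatory decision.

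**What to change.** In Section 6.1 and Table 7:
- Recompute all four columns with one named test, or label the test used in each column.
- State that 71% refers to pooled active versus placebo, and add the power for each dose versus placebo.
- Base the figures on the evaluable patients and events expected from 330 enrolled, and state the assumed non-confirmation, withdrawal and death rates.
- Label the listed hazard ratios as placebo/active, or give them as active/placebo: 1.25, 1.43, 1.67 and 1.11 for medians of 4, 3.5, 3 and 4.5 days.

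The cost is a text edit and one recomputed table. Enrolment, conduct and the planned analyses do not change, and the stated figures become slightly less favourable.

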6.2 SUMMARIES OF CONDUCT OF STUDY

The number of patients who enroll, discontinue (early discontinuation of treatment or early termination from the study), and complete the study will be tabulated by treatment group using descriptive statistics. Reasons for early discontinuation of treatment or early termination from the study will be listed and summarized by treatment group. Any eligibility criteria exceptions and other protocol deviations will also be summarized by treatment group.

6.3 SUMMARIES OF TREATMENT GROUP COMPARABILITY

Demographic and baseline characteristics of the patient will be summarized for all randomized patients by treatment group by use of descriptive statistics. Baseline is defined as the last available value prior to study drug administration.

During the study patient disposition, concurrent treatment, and compliance with study treatment and visits will be summarized on the safety analysis population using descriptive statistics.

6.4 EFFICACY ANALYSES

The primary and secondary efficacy analyses will include all randomized patients who are confirmed to be influenza A infected, with patients grouped according to the treatment assigned at randomization.

Time to event data will be *analyzed* using Kaplan-Meier methodology and stratified Cox proportional hazards models and will be summarized using n, median when estimable, hazard ratios, and 95% confidence intervals. Patients who are lost to follow-up (while event free) will be censored at the time that they are last known to be event free.

The ordinal outcomes will be analyzed using a proportional odds model. To supplement the overall summary odds ratio, separate odds ratios will be estimated for each dichotomized definition of improvement that can be formulated from the components of the ordinal outcome. A test for the proportionality assumption will also be made. Patients discharged from the hospital to a rehabilitation facility will be included in category 5. Patients discharged from the hospital to a nursing home will also be included in category 5, unless the patient lived in a nursing home prior to admission to the hospital, in which case the patient will be characterized based on resumption of normal activities.

Estimation of the treatment difference of proportions and *the corresponding* 95% confidence intervals will be calculated using stratum-adjusted Mantel-Haenszel methodology (Koch et al. 1989). For continuous endpoints, Analysis of Covariance methods (after appropriate transformation of data) will be used to estimate treatment differences and 95% confidence intervals.

Other than censoring in the time to event analyses, no other imputation for missing data will be performed.

